## 12.2 Statistical Analyses

### 12.2.1 Primary Safety Endpoint Analyses

The primary safety composite endpoint is all-cause mortality, disabling stroke, life threatening bleeding requiring transfusion, AKI requiring dialysis, and major vascular complications at 30 days, as adjudicated by the CEC. The proportion of subjects experiencing a primary safety endpoint will be estimated from the binomial model. The 95% confidence intervals will be calculated using the exact Clopper–Pearson method.

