### 1.4 Endpoints

#### 1.4.1 **Primary Safety Endpoint**

Composite of all-cause mortality, disabling stroke, life threatening bleeding requiring transfusion, Acute Kidney Injury (AKI) requiring dialysis, and major vascular complications at 30 days.

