## 2.3 Endpoint Analysis

### 2.3.1 **Primary Endpoints**

#### 2.3.1.1 Primary Safety Endpoint

The primary safety composite endpoint is all-cause mortality, disabling stroke, life threatening bleeding requiring transfusion, AKI requiring dialysis, and major vascular complications at 30 days, as adjudicated by the CEC. COVID-19 relatedness of mortality, disabling stroke, life threatening bleeding requiring transfusion, AKI requiring dialysis, and major vascular complications will be adjudicated by the CEC, and any 30-day mortality, disabling stroke, life threatening bleeding requiring dialysis, and major vascular complications will be excluded from the primary analysis. The proportion of subjects experiencing a primary safety endpoint will be estimated from the binomial model. The 95% confidence intervals will be calculated using the exact Clopper-Pearson method.

The analysis population will include subjects enrolled in the study that is described in Section 2.1.1, including subjects who withdraw or are lost to follow-up prior to 30-day visit.

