#### 2.3.1.2 **Primary Performance Endpoint**

The primary performance composite endpoint is all-cause mortality or disabling stroke at 1 year, adjudicated by the CEC. COVID-19 relatedness of mortality and disabling stroke will be adjudicated by the CEC, and any 1-year death or disabling stroke that is adjudicated as COVID-19 related will be excluded and subjects' follow-up will be censored at the first COVID-19 related event from the primary analysis. The proportion of subjects experiencing a primary performance endpoint will be estimated using the Kaplan-Meier (KM) method, and the standard error of KM estimate will be calculated with Greenwood method.

The analysis population will include subjects enrolled in the study that is described in Section 2.1.1.

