#### 2.8 Handling of Missing Data

All analyses will be performed on available data and additional considerations due to the COVID-19 pandemic are detailed in Section 2.2.4 and in the primary and secondary endpoint sections. This is a retrospective study collecting data that is available per the site standard of care (SOC) and the majority of subjects will be followed for at least 1 year. Therefore, there is no plan to impute missing data.

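### The 30-day safety proportion keeps early leavers in a binomial denominator, so a leaver with no recorded event and unknown day-30 status is in effect scored event-free

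*SAP*

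**What the plan says.** SAP 1.4.1 defines the endpoint as "Composite of all-cause mortality, disabling stroke, life threatening bleeding requiring transfusion, Acute Kidney Injury (AKI) requiring dialysis, and major vascular complications at 30 days". Protocol 12.2.1 and SAP 2.3.1.1 agree on the estimator: "The proportion of subjects experiencing a primary safety endpoint will be estimated from the binomial model". On the interval the SAP says: "The 95% confidence intervals will be calculated using the exact Clopper-Pearson method".

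SAP 2.3.1.1 then sets the analysis population as the subjects of SAP 2.1.1, "including subjects who withdraw or are lost to follow-up prior to 30-day visit". SAP 2.3.1.2 has no such clause for the performance endpoint and uses a different method: "The proportion of subjects experiencing a primary performance endpoint will be estimated using the Kaplan-Meier (KM) method".

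SAP 2.8 states a general rule: "All analyses will be performed on available data". It adds that "there is no plan to impute missing data", and Protocol 12.7 also rules out imputation. The sensitivity analyses in SAP 2.12 concern COVID-19 relatedness and VARC-2 and VARC-3 events. SAP 3.3 tabulates early terminations by visit. Neither document says how to classify a subject who has no recorded event and unknown status at day 30.

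**The concern.** Every subject in a binomial denominator carries a 0 or a 1. If a subject who left before day 30 stays in the denominator and only adjudicated events enter the numerator, that subject scores 0 unless an event was recorded before departure. This is single imputation of no event, although the SAP says that nothing is imputed. If the available-data rule was instead meant to remove such subjects, it conflicts with the clause that includes them. Two programmers could derive different denominators for a primary endpoint from the same text.

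The study tests no hypothesis on its primary endpoints (SAP 2.10), so the estimate and its interval are the primary result. The error runs in the reassuring direction for a safety rate, and no planned analysis would reveal its size.

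**Working it through.** The plan states no expected event rate, no expected early loss and no sample-size calculation, so there is no figure of its own to reproduce.

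**Inputs**
- N = 100, the maximum for the primary analysis population in SAP 1.3.
- x = 10 subjects with an observed event. This is an assumption. For scale, Protocol 2.1 cites a registry with 17 deaths among 202 patients at 30 days (8.4%), which is mortality alone.
- m = 0, 2, 5 or 10 subjects with no recorded event and unknown day-30 status. This is also an assumption, because the documents give no figure.

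**Formulas**
- As written: x/N.
- Known status only: x/(N − m).
- All unknowns counted as events: (x + m)/N.
- Intervals: exact two-sided 95% Clopper-Pearson.

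**Direction.** Let u be the true number of events among the m unknowns, so 0 ≤ u ≤ m. The full-cohort rate is (x + u)/N. The as-written rate x/N can equal this but never exceed it, and the shortfall u/N is at most m/N.

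**Results for N = 100, x = 10**

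| m | As written | Known status | All unknown as events |
|---|---|---|---|
| 0 | 10.0% (4.9 to 17.6) | 10.0% (4.9 to 17.6) | 10.0% (4.9 to 17.6) |
| 2 | 10.0% (4.9 to 17.6) | 10/98 = 10.2% (5.0 to 18.0) | 12/100 = 12.0% (6.4 to 20.0) |
| 5 | 10.0% (4.9 to 17.6) | 10/95 = 10.5% (5.2 to 18.5) | 15/100 = 15.0% (8.6 to 23.5) |
| 10 | 10.0% (4.9 to 17.6) | 10/90 = 11.1% (5.5 to 19.5) | 20/100 = 20.0% (12.7 to 29.2) |

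The as-written column does not change with m, so the reported result carries no trace of the missing information. At m = 5 the interval is 12.7 points wide as written and 13.3 points on known status.

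**Kaplan-Meier check.** The estimate depends on when subjects leave relative to the events. At m = 5:
- All events before the losses: 1 − 90/100 = 10.0%.
- All losses before the events: 1 − 85/95 = 10.5%.
- Six events, then five losses, then four events: 1 − (94/100)(85/89) = 10.2%.

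Kaplan-Meier therefore lies between the as-written and known-status figures. The known-status figure is the upper end because its denominator keeps leavers who had an event and drops leavers who did not.

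**The case against.** The strongest reply is that the SAP never says such subjects count as event-free. The clause says who belongs to the population, and it does a proper job: a subject who had an event and then left should stay in. It also agrees with Protocol 12.1, which takes all enrolled subjects. This stands in part. A reader might infer that the SAP expressly imputes no event and so flatly contradicts SAP 2.8. The text does not go that far. Scoring as event-free is what follows from a full binomial denominator with no stated rule for unknowns, so the two sections are in tension.

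The second reply is that early unknowns should be rare. Procedure and discharge data are already in the records (Protocol 4.1). Patients are approached for consent after the procedure (Protocol 6.3). A missed visit is not a withdrawal, and sites must try the subject and the referring physicians before declaring loss (Protocol 8.2). Data may come by phone, mail or email (Protocol 9), and SAP 2.8 expects most subjects to have at least a year of follow-up. This stands, and it limits the size of the problem. It does not remove it: collection depends on standard of care, and missed data need not be reported as deviations (Protocol Table 3).

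The third reply is that SAP 3.3 already shows early terminations. It does, but a subject who terminated early may have had an event first or have later documented status, so that table does not count unknown 30-day outcomes.

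**Conclusion.** The point holds as a gap in the primary safety analysis. Followed as written, the rate can only equal or understate the full-cohort rate, its interval is slightly too narrow, and nothing planned shows by how much.

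The likely size is modest. With 100 subjects, 10 events and 5 unknown, the rate moves from 10.0% to 10.5% on known status. The 15.0% figure is a worst-case bound and does not estimate the bias. All of these rest on assumed event and loss counts, and with no early losses there is no effect.

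Two stronger readings should be resisted. One is that the safety rate is materially understated: the documents give no loss figure to support that, and there is no hypothesis test to overturn. The other is that restricting the denominator to subjects of known status cures the problem: entry to that denominator depends on the outcome, so it replaces a downward bias with an upward one.

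**What to change.** In SAP 2.3.1.1:
- Keep all subjects of SAP 2.1.1, including leavers who had an event before leaving.
- State that event-free status documented at any later contact counts as known day-30 status.
- Estimate the 30-day rate by Kaplan-Meier with a Greenwood standard error, censoring subjects of unknown status at last contact, as a counterpart to SAP 2.3.1.2. Alternatively, keep the binomial estimate with its Clopper-Pearson interval and add the Kaplan-Meier estimate as a sensitivity analysis.
- Report the number of subjects with unknown 30-day status.

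In SAP 2.12, add one row that counts all of those subjects as events. Do not make the known-status proportion the primary estimate.

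The cost is a few sentences, one count and one or two table rows, with no new data collection. The stated rate may be slightly higher. If Kaplan-Meier becomes the main estimate, the SAP should also say how its interval is formed. With 10 events in 100 and no loss, the standard error is √(0.10 × 0.90/100) = 3.0 points, and a plain symmetric interval would be 10.0 ± 1.96 × 3.0, or 4.1% to 15.9%. Its upper limit is below the exact 17.6%. Keeping the binomial estimate and adding Kaplan-Meier beside it avoids that choice. The rule should be fixed before the data lock so that the denominator is not chosen after the results are known.

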#### 2.3.1.2 **Primary Performance Endpoint**

The primary performance composite endpoint is all-cause mortality or disabling stroke at 1 year, adjudicated by the CEC. COVID-19 relatedness of mortality and disabling stroke will be adjudicated by the CEC, and any 1-year death or disabling stroke that is adjudicated as COVID-19 related will be excluded and subjects' follow-up will be censored at the first COVID-19 related event from the primary analysis. The proportion of subjects experiencing a primary performance endpoint will be estimated using the Kaplan-Meier (KM) method, and the standard error of KM estimate will be calculated with Greenwood method.

The analysis population will include subjects enrolled in the study that is described in Section 2.1.1.

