#### **5.2 Primary Performance Endpoint**

Composite of all-cause mortality or disabling stroke at 1 year.

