### 12.2.2 Primary Performance Endpoint Analyses

The primary performance composite endpoint is all-cause mortality or disabling stroke at 1 year, adjudicated by the CEC. The proportion of subjects experiencing a primary performance endpoint will be estimated using the Kaplan-Meier (KM) method, and the standard error of KM estimate will be calculated with Greenwood method.

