#### 2.12 Sensitivity Analysis

For the primary safety endpoint and performance endpoint, a sensitivity analysis will be conducted including all CEC adjudicated component events regardless of relationship to COVID-19 to assess the impact of the pandemic. Sensitivity analysis will also be conducted including all CEC adjudicated VARC-2 events and VARC-3 events regardless to COVID-19 to assess the impact of the pandemic.

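### The SAP's primary analyses drop COVID-19-related events from composites defined with all-cause mortality, and the 30-day exclusion clause omits its COVID-19 qualifier

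*SAP*

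**What the plan says.** Protocol 5.2 defines the performance endpoint as "Composite of all-cause mortality or disabling stroke at 1 year", and SAP 1.4.2 uses the same definition. Protocol 12.2.2 repeats it ("The primary performance composite endpoint is all-cause mortality or disabling stroke at 1 year, adjudicated by the CEC") and specifies Kaplan-Meier estimation, with no exception for any cause of death. The 30-day safety composite in protocol 5.1 and 12.2.1 and SAP 1.4.1 also contains all-cause mortality with no exception.

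SAP 2.3.1.2 restates the all-cause definition and then says that "any 1-year death or disabling stroke that is adjudicated as COVID-19 related will be excluded" and that "subjects' follow-up will be censored at the first COVID-19 related event from the primary analysis". SAP 2.3.1.1 has the CEC adjudicate COVID-19 relatedness of each safety component. Its list of what is then removed ends with "life threatening bleeding requiring dialysis, and major vascular complications will be excluded from the primary analysis". That list carries no COVID-19 condition.

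SAP 2.2.4 gives the reason for these rules: to limit confounding of the primary endpoints by the pandemic. SAP 2.12 plans a sensitivity analysis of both primary endpoints "including all CEC adjudicated component events regardless of relationship to COVID-19". SAP 2.10 states that no hypothesis is tested.

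**The concern.** A mortality component that leaves out one cause of death is not all-cause. The disabling stroke component carries no all-cause label, but removing some strokes still departs from the composite as defined.

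This is a single-arm study with no hypothesis test, so the point estimate and its interval are the primary result. If the estimate does not measure the endpoint whose name it carries, readers will take it for the all-cause rate. The figure that does match the definition would appear only as a sensitivity analysis.

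The safety section has a further problem. A programmer who followed its exclusion clause word for word would delete most of the endpoint.

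**Working it through.** The documents give no expected event rate and no expected number of COVID-19-related events, so there is no planned figure to reproduce. What follows establishes the direction and illustrates the size.

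**Inputs**
- N = 100, the maximum for the primary population in SAP 1.3.
- 14 composite events by 1 year, with no other censoring. This is an assumption. Its order of magnitude comes from the 85.8% one-year freedom from all-cause mortality that protocol 2.1 reports for an earlier registry, used only to choose a plausible rate.
- c of the 14 events adjudicated as COVID-19 related, c = 0 to 5. This is an assumption.
- The event that triggers censoring is read as a COVID-19-related death or disabling stroke.

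**Direction, 1-year endpoint.** The Kaplan-Meier survival estimate is the product of (1 − 1/r) over event times, where r is the number at risk. Turning an event into a censoring at the same time removes one factor below 1 and leaves every other risk set unchanged. Survival can only rise, so the event rate can only fall. A check on 20,000 simulated data sets found no exception.

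**Size, 1-year endpoint.** With all 14 events counted, the product telescopes to 86/100, giving a rate of 14.0% (Greenwood SE 3.47 points). If c events are censored:
- when they are the earliest c, survival = 0.86 × 100/(100 − c);
- when they are the latest c, survival = 0.86 × (86 + c)/86 = (86 + c)/100.

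| c | Rate, earliest events censored | Rate, latest events censored |
|---|---|---|
| 0 | 14.00% | 14.00% |
| 1 | 13.13% | 13.00% |
| 2 | 12.24% | 12.00% |
| 3 | 11.34% | 11.00% |
| 4 | 10.42% | 10.00% |
| 5 | 9.47% | 9.00% |

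The fall per event runs from 14.00 − 13.13 = 0.87 to 14.00 − 13.00 = 1.00 point. At c = 5 it is (14.00 − 9.47)/5 = 0.91 to (14.00 − 9.00)/5 = 1.00.

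**Size, 30-day endpoint.** Assume 10 events in 100, of which 2 are excluded as COVID-19 related. All events: 10/100 = 10.0% (Clopper-Pearson 95% CI 4.9 to 17.6). If the two subjects stay in the denominator as event-free: 8/100 = 8.0% (3.5 to 15.2). If they are removed: 8/98 = 8.2% (3.6 to 15.5). The rate is lower either way. SAP 2.3.1.1 keeps subjects who withdraw or are lost before 30 days, but does not say explicitly how subjects with an excluded event are counted.

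**Wording of 2.3.1.1.** The sentence first names five components for adjudication: mortality, disabling stroke, bleeding requiring transfusion, AKI requiring dialysis and major vascular complications. The exclusion list that follows has four items. Bleeding and AKI have become one item, bleeding requiring dialysis, which is not a component of the endpoint. The corresponding clause in 2.3.1.2 limits exclusion to events adjudicated as COVID-19 related; this one does not. Taken literally, it removes every 30-day death, disabling stroke and major vascular complication, and leaves the handling of COVID-19-related bleeding and AKI undefined.

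**The case against.** The best defence is that the sponsor has prespecified a COVID-free estimand, with a stated reason and independent adjudication of relatedness. Censoring at the COVID-19 event is a recognised approach to such an estimand if censoring is non-informative. The all-events result is also prespecified in SAP 2.12, and all-cause mortality at 30 days and 1 year is a descriptive endpoint with no stated exclusion. No performance goal or test depends on the rate.

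Much of this stands. The all-cause figures should be available, and no formal decision changes. But a COVID-free estimand needs its own name, non-informative censoring is doubtful in patients chosen for increased surgical risk, and with no comparator arm there is no between-group contrast to protect from confounding. A sensitivity analysis does not correct a primary result that differs from its own definition.

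Several stronger readings are tempting but unsupported:
- *The estimate is biased low without qualification.* It is low only against the all-cause definition, and only if at least one COVID-19-related event occurs.
- *The protocol requires COVID-19 events to be counted.* Protocol 12.2 is silent on COVID-19, and section 12 leaves further analysis detail to the SAP. The conflict is with the endpoint definition.
- *The rate loses comparability with the registry figures in protocol 2.1* (8.4% mortality at 30 days, 85.8% one-year freedom from death). These are background, not benchmarks. They cover mortality alone, and that registry began in 2010, before COVID-19.
- *An unrelated death after a COVID-19-related stroke is an additional loss.* The subject would already have counted once, at the stroke.
- *The sponsor means to delete all 30-day events.* The start of the sentence, 2.3.1.2 and 2.12 show the intent. It is a drafting slip, though in the text that governs a primary analysis.

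**Conclusion.** The point holds as a mismatch between label and analysis, together with a drafting error. As written, the primary performance rate is not the defined composite and lies below it whenever a COVID-19-related death or disabling stroke occurs. The gap is about 0.9 to 1.0 percentage point per such event, assuming 100 subjects, 14 events and no other censoring. One event would move the estimate by roughly a quarter of its standard error (0.87/3.47 = 0.25 to 1.00/3.47 = 0.29); five would move it by 4.5 to 5.0 points. With none, the two analyses agree. The documents give no basis for predicting the number.

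The safety endpoint has the same mismatch, with an exclusion clause that cannot be followed as written and a denominator that is not stated explicitly. The sponsor should correct both sections. No test or success criterion is affected.

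**What to change.** 1. In SAP 2.3.1.1 and 2.3.1.2, make the primary analysis count all CEC-adjudicated component events, as SAP 2.12 already plans, so that it matches the endpoint definitions. Move the COVID-19-excluded analysis to 2.12 as the sensitivity analysis, do not label it all-cause, and align 2.2.4.
2. In the 2.3.1.1 exclusion text, wherever it ends up, restore the condition that the event was adjudicated as COVID-19 related. List life-threatening bleeding requiring transfusion and AKI requiring dialysis as separate items. State whether subjects with an excluded event stay in the denominator as event-free or are removed.
3. In the censoring rule, say that the triggering event is a COVID-19-related death or disabling stroke.

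If the sponsor keeps the COVID-19-excluded analysis as primary, the endpoint should be renamed in both the SAP and the protocol; item 2 is needed in any case.

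The swap costs SAP wording only: both analyses are already planned and no new data are needed. The headline rate becomes slightly less favourable if any COVID-19-related event occurs. The renaming route also needs a protocol amendment.

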### 2.3.2 **Descriptive Endpoints**

Descriptive endpoints are listed in Section 1.4.3. Study results will be summarized using descriptive statistics including mean, standard deviation, median and range for continuous data and count and percentage for categorical data. All analyses will be performed on available data.

#### 2.3.3 Exploratory Registry Arm

The data collected from subjects in the exploratory arm will not be included in the primary analysis but will be analyzed using descriptive statistics. Data from this analysis may be used to explore future research, specifically on valve sizing and echocardiogram measurements (eg. PVL, TVL, etc.).

The analysis population will include subjects enrolled in the study that is described in Section 2.1.2.

#### 2.4 Sample Size Calculations

It is anticipated that up to subjects may be enrolled in the primary analysis population. Additional subjects that have undergone an attempted Portico ViV implant may be analyzed. The exploratory registry arm will have no limit on the number of enrolled subjects.

#### 2.5 Interim Analysis

No formal statistical rule for early termination of the trial is defined. Interim study reports may be produced for regulatory or reimbursement purposes.

#### 2.6 **Timing of Analysis**

The primary endpoints analyses will be conducted on datasets locked after approximately subjects completed their 1-year follow-up excepting deaths, withdrawals and loss to follow-up before 1-year or crossed the 1-year visit window without a visit (missed visit).

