## 9 DATA COLLECTION AND EVALUATION OF ENDPOINTS

The Principal Investigator is responsible for ensuring all study data is collected as required per the protocol scheduled time points. In addition to accessing the subject's medical records, data collection may also occur remotely by phone contact, mail, in-person, or through email. The clinical study will be conducted in accordance with the protocol. All parties participating in the conduct of the study will be qualified by education, training and/or experience to perform their tasks. This training will be documented appropriately. The data collection elements required for each follow-up are listed below and in **Table 3** below.

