**Table 3: Data Collection Overview**

Visit Activity or Information Collected	Initial Data Collection			Follow-Up Data Collection					
	Baseline	Procedure	Discharge	30-Day	1 Year	2 Year	3 Year	4 Year	5 Year
Demographics	X								
Medical History	X								
Lab measurements*	X			X					
Clinical Assessment with physical exam ^			X	X	X	X	X	X	X
Cardiovascular Medications (examples: cardiac medications and blood thinners)	X			X	X	X	X	X	X
NYHA Classification β	X			X	X	X	X	X	X
Transthoracic Echocardiography (TTE) or Transesophageal Echocardiography (TEE) γ	X		X	X	X	X	X	X	X
Procedure details		X							
Adverse Events, Device Deficiency, and Withdrawal Σ		X	X	X	X	X	X	X	X
Reintervention Procedure (if applicable)			X	X	X	X	X	X	X
Protocol Deviations related to informed consent process or inclusion/exclusion criteria, or safety reporting requirements (if applicable)	X	X	X	X	X	X	X	X	X

\*Blood tests that are standard of care; βNYHA will be determined from signs and symptoms observed attributed to heart function and can be calculated from medical records. ^Clinical assessment will assess general health and information on any new diagnostics, treatments, or tests since the last visit. ΣIf applicable; γEchocardiograms submitted to the Echo Core Lab should be imaging medium but may be provided as a report if imaging is not available to submit to the core lab.

Note: Neurologic assessments will be collected for any neurologic event (if applicable) and may be assessed from available medical records.

In the event that more than 1 echocardiogram or required data point is performed and available within a specific study data collection timepoint, the data closest to the study timepoints will be used for the primary analysis. However, all available data should be collected in additional applicable CRFs. Additional echocardiograms should be submitted to the echocardiogram core lab for analysis. Data may be collected based on availability from SOC and protocol deviations for out of window/missed visit or out of window/missed data will not be required.

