#### 1.3 **Clinical Investigation Design**

This is a multi-center, international, single-arm, retrospective data-collection study. The study will use a Core Laboratory for echocardiogram analysis and a Clinical Events Committee (CEC). The study includes the primary study arm and an exploratory registry arm; both study arms will follow all timepoints and data-collection requirements outlined in Figure 2 of the CIP. This study may include up to 100 patients for the primary analysis population.

Patients must have met the sizing requirements of the PorticoTM transthoracic aortic valve sizing specification ( $\geq$ 19 mm and  $\leq$ 27 mm). Patients must meet all inclusion and exclusion criteria to be eligible for enrollment.

In addition, an exploratory registry arm will collect data for patients that were treated for a failed surgical bioprosthetic aortic valve true inner diameter size of <19 mm or >27 mm. There will be no enrollment limit in the exploratory registry arm.

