#### 2.2.3 Survival Analyses

Survival analysis will be conducted to analyze time-to-event variables. Subjects without events will be censored at the time of analysis. Survival curves will be constructed using Kaplan-Meier estimates and Greenwood standard errors.

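### The 1-year lock can proceed on missed visits before vital and stroke status is traced, and SAP 2.2.3 read literally then treats unknown status as event-free

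*SAP*

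**What the plan says.** SAP 2.6 triggers the lock once a set number of subjects (missing from the public text) have completed 1-year follow-up. It excepts subjects who died, withdrew, were lost "or crossed the 1-year visit window without a visit (missed visit". Protocol 12.4 has the same rule. Neither section mentions status at or after day 365.

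The performance endpoint is death from any cause or disabling stroke by 1 year. It "will be estimated using the Kaplan-Meier (KM) method" (SAP 2.3.1.2). The censoring rule is in SAP 2.2.3: "Subjects without events will be censored at the time of analysis".

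On missing data, SAP 2.8 says "Therefore, there is no plan to impute missing data", on the ground that "the majority of subjects will be followed for at least 1 year". The sensitivity analyses in SAP 2.12 vary only COVID-19 relatedness and the VARC-2 and VARC-3 event sets.

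Two protocol provisions bear on tracing. Section 8.2 requires calls, a registered letter and efforts to reach the local or referring physician when a subject cannot be reached and the records are insufficient. Section 9 adds that "data collection may also occur remotely by phone contact, mail, in-person, or through email". The notes to Table 3 say that "protocol deviations for out of window/missed visit or out of window/missed data will not be required".

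**The concern.** Data come from standard-of-care visits. A patient who died elsewhere, or who is too disabled by a stroke to travel, may appear in the database simply as a missed 1-year visit. If the lock proceeds before anyone has asked, that outcome stays unknown.

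The censoring rule then decides what the unknown becomes. Kaplan-Meier would normally censor such a subject at last contact. Censoring at the time of analysis places the subject in the risk set as event-free through day 365, which pulls the estimated event rate down. Even censoring at last contact is unbiased only if those who drop out of sight have the same risk as those who do not.

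The study tests no hypothesis (SAP 2.10), so the 1-year rate is itself the result. Nothing planned would show a reader how much of it rests on unknown outcomes. Missed visits generate no deviation reports, and the early-termination summary in SAP 3.3 need not include subjects who missed a visit, because Protocol 8.2 keeps them in the study.

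**Working it through.** The plan has no figure to reproduce: it states no power, margin, dropout share or sample-size derivation. The check is therefore an illustration.

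**Inputs**
- N = 100. SAP 1.3: "This study may include up to 100 patients for the primary analysis population".
- Event rate 14.2%. Protocol 2.1 cites 85.8% freedom from death at 1 year in a global ViV registry, and 100 − 85.8 = 14.2. That figure is death only; using it for death or disabling stroke is an assumption.
- m, the number with unknown 1-year status. The documents do not give it; 5 to 20 is assumed.

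**Step 1: sampling error with status complete.** For 14 events in 100, the exact (Clopper–Pearson) 95% interval is 7.9% to 22.4%, a width of 14.5 points. With nobody censored before 1 year, the Greenwood half-width is 1.96 × √(0.142 × 0.858 / 100) = 6.8 points, or 13.7 points in full, so the yardstick hardly changes.

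**Step 2: bounds from unknown status.** Events among those known: e = round(0.142 × (100 − m)). Lower bound e/100 (no unknown subject had an event); rate among known e/(100 − m); upper bound (e + m)/100 (every unknown subject had an event).

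| m | e | Lower | Among known | Upper |
|---|---|---|---|---|
| 5 | 13 | 13% | 13.7% | 18% |
| 10 | 13 | 13% | 14.4% | 23% |
| 15 | 12 | 12% | 14.1% | 27% |
| 20 | 11 | 11% | 13.8% | 31% |

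The width is m points, so it passes 14.5 points from m = 15.

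**Step 3: effect of the censoring date.** This used 1,500 simulated studies of 100 subjects with exponential event times, where 20% of subjects had no information after day 30.

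| 1-year risk in the unknown, relative to the others | True rate | KM, censored at last contact | KM, censored at analysis |
|---|---|---|---|
| 1× | 14.2% | 14.2% | 11.6% |
| 2× | 17.0% | 14.4% | 11.9% |
| 3× | 19.8% | 14.7% | 12.2% |

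The first row can be checked by hand. By day 30 the unknown group shows 1 − 0.858^(30/365) = 1.25% events, so the rate censored at analysis is 0.8 × 14.2% + 0.2 × 1.25% = 11.6%.

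Censoring at last contact removes the bias when risks are equal. When they differ, only obtaining the status removes the rest.

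**The case against.** The strongest reply is that much of the tracing is already required. Protocol 8.2 demands documented calls, a letter and attempts through physicians. Protocol 9 makes the investigator responsible for collecting data at the scheduled time points, sites must report deaths, strokes and all serious events (Protocol 11.6), and centralized monitoring looks for missing data (Protocol 15.4). This stands, and it rules out any claim that the plan makes no check of status. What remains is timing. The 8.2 effort leads towards declaring a subject lost, while SAP 2.6 lists losses and missed visits separately, and 8.2 itself says that a subject who missed a visit may return later. Such a subject can reach the lock without completed tracing.

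Second, a missed visit is not the same as unknown status. The study is retrospective: anyone who personally consents after day 365, or is contacted or recorded later, is known to have been alive at 1 year. This also stands. It confines the problem to subjects with no contact or record at or after day 365, and to stroke status where later contact does not settle it.

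Third, data-management text, visit windows and the lock number are redacted, so any statement that a requirement is absent covers visible text only.

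Some stronger inferences are tempting but unsupported:
- That a missed visit counts as complete. SAP 2.6 makes it an exception in the lock trigger and does not say how the subject is analysed.
- That the reference to a majority accepts nearly half missing at lock. In SAP 2.8 it supports only the decision not to impute.
- That waiving deviation reports causes the gap. A deviation entry would recover no outcome.

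**Conclusion.** The point holds in limited form. The lock can proceed without documented 1-year status for subjects with a missed visit. The literal censoring rule would count those truly unknown as event-free, and no planned analysis examines them. The likely direction is a 1-year rate that is too low.

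The size cannot be taken from the documents. On the assumptions above, 20% unknown after day 30 lowers the estimate from 14.2% to 11.6% through the censoring rule alone. The bounds are extreme by construction, since the upper one requires every unknown subject to have died or had a disabling stroke. A reader comparing upper limits alone (23% against 22.4%) might infer that 10 unknown already matches sampling error. By width it is 10 points against 14.5, and about 15 unknown are needed.

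A reader might also extend the point to both primary endpoints. The 30-day safety endpoint does not depend on the 1-year visit. This is an inexpensive improvement to the plan, best made before the lock.

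**What to change.** 1. In SAP 2.6 and Protocol 12.4, require that before lock the methods in Protocol 8.2 and 9 (records, phone, referring physician) are used to document vital and stroke status at or after day 365. This applies to each primary-population subject with a missed 1-year visit and no later contact. Events found this way go to the CEC. A stroke that cannot be graded for disability, because the 90-day mRS in Appendix B is lacking, stays in the unknown count.
2. In SAP 2.2.3, censor subjects without an event at the last date on which their event-free status is known.
3. In SAP 2.12, report the number still unknown at 1 year and add a bounding analysis of the performance endpoint that counts them all as events and then all as non-events.

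The cost is a call or record query per affected subject, one table and possibly a short delay to the lock. The documents do not say how easily status can be obtained, only that the contact methods are permitted.
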